The primary objective of this proposal is to add to the palette of treatment options by comparing the effect of two opioid dependence treatment delivery models on improving the HIV care engagement and outcomes in Vietnam. We propose a multisite, open-label, randomized, flexible-dose noninferiority trial of buprenorphine/naloxone (BUP/NX) (n=225) versus methadone maintenance therapy (MMT) referral (n=225) for treatment of opioid dependence in HIV-infected participants in 6 Vietnam HIV clinic research sites. The study is conducted in partnership with colleagues at Hanoi Medical University (HMU), the Provincial AIDS Control (PAC) authorities of Hanoi, Thanh Hoa, and Bac Giang, the Vietnam National Institute of Mental Health, and Oregon Health & Science University.

Study sites are 4 HIV clinics in Hanoi, 1 in Thanh Hoa, and 1 in Bac Giang; epicenters of Vietnam's HIV and heroin epidemics, all of which are associated with MMT and HIV testing and counseling centers. A research coordinating center at HMU provides additional outreach, recruitment, non-medication-related study procedures and links participants to participating HIV clinic sites for clinical management. HIV providers will be trained to manage opioid dependence using BUP/NX.

Participants are HIV-infected participants with opioid dependence new to HIV care, recruited from HIV clinics, MMTs, and associated HIV testing centers. Participants randomized to BUP/NX will receive BUP/NX after successful completion of medication induction and stabilization. Participants randomized to BUP/NX will receive a taper after 12 months of study drug exposure, with referral for MMT. Participants randomized to MMT will receive usual care, which is case-manager-assisted referral to MMT. All participants receive clinic-based individual counseling and HIV care.

The primary outcome of HIV-1 viral load will be measured at baseline, 6, and 12 months. Secondary outcomes, including self-reported drug use, urine drug screens (UDS), and measures of HIV care engagement (adherence, retention) will be assessed quarterly through 12 months follow-up. Qualitative interviews with participants, family members of participants, and providers in years 1 through 4 will identify lessons-learned for scale-up of HIV clinic-based BUP/NX.

Figure 2. Study Schema

There are three specific aims in this protocol:

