Adverse Events • Paper Log • eCRF • Serious Adverse Events eCRF								X
Protocol Deviation • Paper Log • eCRF								X

Table 2: Table of Assessments								
	Pre-Screening	Screening	Baseline	3 Month	6 Month	9 Month	12 Month	As Needed Only
Study Termination Form							X	X (if ppt ends early)
*chart abstraction possible								

Visit Procedures

Survey Data

Research assistants will administer participant surveys in a confidential setting using real-time, secure, web-based electronic data entry. All survey measures have been translated into Vietnamese and been field tested and adapted for cultural appropriateness and feasibility for electronic data collection in Vietnam during previous research.

Survey data measurements include:

- Demographics
- Drug and alcohol use
- Addiction treatment
- HIV treatment
- Co-morbid conditions including physical and mental health
- Quality of life

Medical Chart Data

Research assistants will review participant HIV clinic and MMT medical charts quarterly to inform outcome measures including receipt of ART, retention in care, and adherence to study treatment condition (buprenorphine, methadone dosing, counseling visits). Medical charts will be reviewed at Baseline to establish diagnoses of Hepatitis B, Hepatitis C, and Tuberculosis. If not available in medical chart, research staff will obtain testing as necessary.

Biologic Data

Urine samples for pregnancy and urine drug screens (morphine, methamphetamine, methadone, amphetamine, buprenorphine) will be collected and processed in the HIV clinic using point of care testing.

Viral load specimens will be drawn at baseline, 6, and 12 months, and processed for transport at HIV clinic, then transported to the National Hospital for Tropical Disease for centralized lab testing. HIV viral load testing (the primary outcome) is performed with Real-time RT-PCR on Real-time ABI 7500 machine with reagents and primers made by Invitrogen.¹¹⁰ The current viral load technique is certified for a lower limit of HIV-1 RNA detection of 55 copies/mL.

All other phlebotomy measurements (Safety Labs, and CD4) will be either drawn at the appropriate times following the above schedule or will be chart-abstracted as required. They will be drawn and processed for analysis at the HIV clinic locally.

Study physicians will conduct baseline physical exams to assess for medical appropriateness for participation.

Qualitative Data

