HIV clinic providers and staff will be trained in BUP/NX management of opioid dependence. Participants randomized to clinic-based BUP/NX will be evaluated by the HIV clinic study physician for symptoms and signs of withdrawal using clinically available opioid withdrawal scales and induced onto BUP/NX when in moderate withdrawal in order to avoid precipitated withdrawal (12-24 hours after last dose of short-acting opiates like heroin, and 2-4 days after last dose of long-acting opioids. BUP/NX induction begins with a 2-4 mg test dose followed by additional doses on the day of induction to relieve withdrawal symptoms, and then titrated to a maintenance dose between 8-24 mg/day over 1 to 3 days. Participants will return for daily dosing until a stable maintenance dose is reached, as determined clinically by the HIV clinic study physician. Dosing will remain flexible to a maximum dose of 24mg. After a participant is stabilized on a maintenance daily dose for at least 2 weeks, they may switch to every-other-day dosing (4 times per week), doubling the maintenance dose to a maximum of 32mg prior to “skip” days. Participants will continue to receive BUP/NX for 12 months, followed by a 14-day taper and referral to MMT. The study will use BUP/NX in a 4:1 ratio combination sublingual tablet for treatment of opioid dependence.

Referral for MMT

Referral for MMT has become the standard of care for opioid dependence in Vietnam. Participants randomized to MMT referral will meet with an HIV clinic case manager who will facilitate referral to MMT. Methadone dosing will be managed by MMT staff, who dispense methadone according to Ministry of Health guidelines for MMT.⁹⁸

[figure not shown]
Study sites and dosing sites

Participants will complete all research activities (consenting, surveys, and other data collection activities) at the six HIV clinics. Two HIV clinics (Tu Liem clinic and Long Bien clinic) will serve only as clinical management and medication dispensing sites, with non-medication study procedures being performed by Vietnam Research Coordinating Center (HMU) research staff.

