The study staff will be trained to monitor for and report Adverse Events and Serious Adverse Events. For the purposes of this study, all Serious Adverse Events will require reporting in the data system. Adverse Events that are determined to be Mild and Not Causally Related to Study Drug will not be reported in REDCap™ but will be tracked on a paper log at each site which the Quality Assurance monitors will review at all site visits.

Local research assistants will be responsible for data collection. The PI and Quality Assurance Monitor will work with the study personnel to verify data accuracy via monthly internal data audits.

See separate Data and Safety Monitoring Plan for more information.

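### No adverse event query is scheduled for both arms, and only BUP/NX is dosed at the study clinic, so non-serious events are at risk of unequal ascertainment

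*Combined protocol and SAP*

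**What the plan says.** All references are to the combined protocol and SAP.

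- **Schedule.** In Table 2 (Table of Assessments) the row "Adverse Events • Paper Log • eCRF • Serious Adverse Events eCRF" has a single mark, under *As Needed Only*. The drug screens, dosing forms and HIV care utilization form are marked at 3, 6, 9 and 12 months. The CBC and AST/ALT safety labs are marked at screening only. The section Survey Data does not list AEs as a domain.
- **BUP/NX arm.** Under Clinic-based BUP/NX, participants are induced and dosed at the HIV clinic under its study physician, daily at first. After stabilization "they may switch to every-other-day dosing (4 times per week").
- **MMT arm.** Under Referral for MMT: "Methadone dosing will be managed by MMT staff, who dispense methadone according to Ministry of Health guidelines for MMT".
- **Charts.** Under Medical Chart Data, HIV clinic and MMT charts are reviewed quarterly for outcome measures such as ART receipt, retention and treatment adherence. AEs are not named.
- **Database filter.** Under Data and Safety Monitoring: "Adverse Events that are determined to be Mild and Not Causally Related to Study Drug will not be reported in" REDCap. These events "will be tracked on a paper log at each site which the Quality Assurance monitors will review at all site visits". The same section states that "all Serious Adverse Events will require reporting in the data system".
- **Use of the term.** The Objectives section speaks of study drug exposure in the BUP/NX arm: "Participants randomized to BUP/NX will receive a taper after 12 months of study drug exposure, with referral for MMT". The opening of the Risks section instead refers to study medication in either arm.

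**The concern.** When nobody is scheduled to ask about AEs, capture depends on who happens to see the participant and whether that person fills in study forms. Here that differs by arm: the BUP/NX dosing contact takes place at the study clinic, and the methadone dosing contact takes place in an outside program. Arm is known to everyone, so both noticing an event and judging its cause can be influenced by it.

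The safety board reviews accumulating safety data and can recommend halting the trial, and the results are meant to inform national scale-up of BUP/NX alongside methadone. If non-serious events are recorded more completely in one arm, a summary by arm can show a difference that reflects detection rather than treatment. Events that were never asked about cannot be reliably recovered at analysis.

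**Working it through.** The plan states no AE rate, safety power or safety sample size, so there is no figure to reproduce. The check is a like-for-like comparison of the routes by which an event can reach a study form.

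**1. Contacts over 12 months, assuming full attendance**

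| Contact | BUP/NX | MMT |
|---|---|---|
| Follow-up research visits (Table 2) | 4 | 4 |
| Dosing contacts | 4 × 52 = 208 if dosed 4 times weekly throughout; 7 × 52 = 364 if daily throughout | up to 7 × 52 = 364 (daily observed dosing, Risks section on methadone) |
| Who observes dosing | HIV clinic, under its study physician | MMT program staff |
| HIV care and counseling at the HIV clinic (Objectives) | yes, frequency not stated | yes, frequency not stated |
| Quarterly chart review | yes, AEs not named | yes, AEs not named |

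The number of contacts does not separate the arms: a participant engaged in MMT may have as many as, or more than, a BUP/NX participant. What separates them is whether the observer has a stated link to the study's AE forms. Because the MMT arm is a referral, a participant who never links to a program has no dosing contact at all.

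**2. Reach of the database filter**

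| Event | Entered in REDCap? |
|---|---|
| Mild and unrelated to *Study Drug* | No; site paper log, reviewed by monitors |
| Mild and related | Yes |
| Moderate or severe, non-serious | Yes, whatever the causality |
| Serious | Yes, whatever the causality |

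If *Study Drug* means BUP/NX only, a mild methadone effect counts as unrelated and stays on paper, while the same mild effect of BUP/NX is entered. If it means the assigned treatment, the rule is symmetric. The text supports either reading. Objectives, and the hospital and home dosing paragraph under Study sites and dosing sites, use the term for BUP/NX. The Risks section uses study medication for both arms. The asymmetry is confined to mild events.

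**3. Serious events**

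Risk of Underlying Conditions puts HIV complications, detoxification admissions, hospitalizations and deaths on study-specific forms in both arms, not duplicated as AEs or SAEs, and still sends them to the safety board. Data and Safety Monitoring requires all SAEs in the data system. Table 2 names a Fatal Overdose Form, also *As Needed Only*, but no form named for hospitalizations. The two sections need to be reconciled.

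**4. How unequal capture would act**

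Observed rate = true rate × capture probability. With equal true rates, the false difference = true rate × (BUP/NX capture − MMT capture). The documents give none of these values. Purely as an assumption, take a true rate of 20% in both arms, 225 per arm and 90% capture on BUP/NX:

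| Assumed MMT capture | Observed rates, BUP/NX vs MMT | False difference | Chance of p < 0.05 (two-sided) |
|---|---|---|---|
| 90% | 18% vs 18% | 0 points | 5% |
| 70% | 18% vs 14% | 4 points | about 21% |
| 50% | 18% vs 10% | 8 points | about 69% |
| 30% | 18% vs 6% | 12 points | about 98% |

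At a true rate of 10%, the last three rows become 2, 4 and 6 points, with chances of about 12%, 38% and 77%. The range starts at no bias, and nothing in the documents says where in it the trial would fall.

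**The case against.** A reader might infer that MMT participants are seen only quarterly while BUP/NX participants are seen several times a week. The documents do not support that. Quarterly describes the research visits, which are the same in both arms; methadone dosing is observed daily, and everyone receives HIV care and counseling at the HIV clinic. Nor is every BUP/NX dosing contact a research contact: at two of the six clinics, coordinating center staff carry out the non-medication procedures.

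A reader might also infer that a planned safety comparison is already biased. The Data Analysis section specifies no AE estimate or test by arm. The supported statement is a risk of bias if AE counts are set side by side, as a safety board would ordinarily do.

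The filter, too, could be read as dropping methadone's recognized risks. It removes only events that are both mild and unrelated, and those stay on a monitored log.

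The strongest remaining objection is that an AE log is naturally completed when an event occurs; protocol deviations are marked the same way. Progress notes and visit checklists are scheduled at each follow-up visit, the survey covers physical and mental health, and the separate Data and Safety Monitoring Plan may set out how AEs are solicited. This stands as a reason for caution: the documents do not show that nobody asks. They also do not show that anyone must, and they leave AEs seen by MMT staff without a stated path into the study.

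**Conclusion.** The point holds as a risk of unequal ascertainment of non-serious AEs. It rests on four things the documents show: an event-driven AE row with no common scheduled query, dosing at the study clinic in one arm and by outside staff in the other, a chart review not described as covering AEs, and open-label assessment. The likely direction is relative over-counting on BUP/NX. That is a judgment about who is placed to record events, not a demonstrated result.

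The undefined *Study Drug* is a secondary issue that affects mild events only. The size of any bias cannot be determined from the documents; it would be nil if capture were equal. The conclusion would weaken if the Data and Safety Monitoring Plan already requires the same AE inquiry in both arms, in which case Table 2 should say so. The change is worth making because it is cheap and serves data on which a decision to halt could rest.

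**What to change.** 1. In Table 2, mark the AE/SAE row at 3, 6, 9 and 12 months for both arms, with one standard AE question asked in the same words.
2. Under Medical Chart Data, add AEs and overdoses to the items abstracted quarterly from the HIV clinic and MMT charts.
3. Under Data and Safety Monitoring, replace *Study Drug* in the filter with *assigned opioid treatment (BUP/NX or methadone)*.
4. Label each AE by source (scheduled query, chart, between visits), so that any summary by arm can be shown on the commonly ascertained events, with the others alongside.
5. Reconcile Risk of Underlying Conditions with Data and Safety Monitoring on whether hospitalizations and deaths are reported as SAEs, and name the form that carries hospitalizations.
6. Align all of this with the Data and Safety Monitoring Plan.

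Mild unrelated events can stay on the paper log, provided relatedness is judged against the assigned treatment in both arms.

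The cost is a few minutes at visits that already take place, modest extra data entry and a higher recorded AE count. Quarterly recall will miss some mild events, but the same question at the same times gives both arms the same opportunity to report.

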Participants are randomized to clinic-based BUP/NX vs. referral for MMT. This is a non-blinded study. Randomization will be conducted by computer generated random number sequence in blocks of 10 prepared by statisticians at OHSU. Allocation assignments will be maintained in sealed, sequentially numbered envelopes by the Vietnam Research Coordinating Center (RCC) at Hanoi Medical University. HIV clinic site research assistants will call the RCC to receive allocation assignment when a participant is deemed eligible for study participation.

Pilot Data Collection and Assessments

The data collection instruments were pilot-tested with participants at four additional sites: Bac Giang PAC OPC; Bac Giang Provincial Hospital OPC; Viet Tri, Phu Tho PAC OPC; and Phu Tho Town Community Health Center OPC.

Table 2: Table of Assessments								
	Pre-Screening	Screening	Baseline	3 Month	6 Month	9 Month	12 Month	As Needed Only
Visit Window	--	60 days after Pre-Screening		+/- 14 days	+/- 14 days	+/- 14 days	-14 days/+30 days	--
Pre-Screening Consent Form	X							
Informed Consent		X						
Informed Consent Quiz		X						
Progress Note		X	X	X	X	X	X	X
Visit Checklist	X	X	X	X	X	X	X	
Locator Form	X	X	X	X	X	X	X	
Master Enrollment Log	X	X	X					
Communication Log								X
Compensation 
 • Log • Receipt 		X	X	X	X	X	X	
Data Collection Forms								
Inclusion/Exclusion Criteria (Eligibility Checklist)			X					
Pre-Screening Survey	X							
Screening Survey		X						
Baseline Survey			X					
3 Month Survey				X				
6 Month Survey					X			
9 Month Survey						X		
12 Month Survey							X	
ASI-lite Table			X	X	X	X	X	
Randomization Form			X					
Physical Exam			X					
Dosing Form 
 • BUP/NX • MMT 				X	X	X	X	
HIV Care Utilization Form				X	X	X	X	
Fatal Overdose Form								X

Table 2: Table of Assessments								
	Pre-Screening	Screening	Baseline	3 Month	6 Month	9 Month	12 Month	As Needed Only
Pregnancy and Birth Control Assessment • Includes Urine Test		X	X	X	X	X	X	
Confirmed Pregnancy Test								X
Early End of BUP/NX								X
HIV Viral Load			X		X		X	
CD4*		X*			X*		X*	
HIV genotype resistance testing (as necessary)			X				X	
HIV confirmatory testing (as necessary)		X						
HIV rapid testing	X							
Tuberculosis (PPD Skin Test)*			X*					
Hepatitis B/C*			X*					
Safety Labs* • CBC • AST/ALT •		X*						
UDS • Morphine • Methadone • Methamphetamine • Amphetamine • Buprenorphine	X	X		X	X	X	X	

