The study will use BUP/NX in a 4:1 ratio combination sublingual tablet for treatment of opioid dependence. Potential adverse events related to BUP/NX include: death, which has been reported among people who abuse BUP in combination with benzodiazepines and other drugs; withdrawal, if BUP is taken while actively taking methadone or various other opioids; increased risk of opioid dependence with continued use of heroin or other opioids; and possible impairment of mental or physical abilities for at least 6 hours after taking BUP.

Because it is a partial opioid agonist, BUP/NX has limited respiratory depressant effects, low toxicity even at high doses, and limited risk of overdose. At sufficient doses, BUP/NX blocks the effects of exogenous opioids and can both reduce illicit use and afford some level of protection against overdose. BUP/NX has abuse potential, though in contrast to full agonists like methadone, this is limited, likely also a consequence of partial agonist properties. Buprenorphine itself may cause physical dependence. It can also cause intoxication and mild respiratory depression, as evidenced by possible drowsiness and breathing that is slower and shallower.

Common side effects from BUP may include headache, constipation, difficulty sleeping, weakness, sleepiness, nausea, vomiting, sweating, and dizziness. Elevated liver enzyme levels have been reported in participants with hepatitis who are treated with buprenorphine.

If the participant attempts to dissolve and inject BUP, he/she may experience opioid withdrawal symptoms, including nausea, diarrhea, hot and cold sweats, hot flashes, muscle cramps, flushing, painful joints, yawning, restlessness, watery eyes, runny nose, chills, gooseflesh, sneezing, abdominal cramps, irritability, backache, tension and jitteriness, depression, sleepiness, shaking or tremor, sensitivity to noise, clammy or damp skin, or other unpleasant

effects. Use of other opioids while receiving the BUP tablet could also result in opioid withdrawal symptoms.

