Though BUP/NX is metabolized by cytochrome P-450 3A4, a prime pathway for antiretroviral metabolism, clinically significant drug-drug interactions with HIV or TB-related treatments are rare. Known P450 inhibitors such as erythromycin, ketoconazole, and the HIV protease inhibitor atazanavir can increase BUP levels. Despite this, there was no difference in mean BUP/NX dose and no episodes of over-sedation among the BHIVES clinical trial participants taking atazanavir versus a non-atazanavir regimen after 12 months of follow-up. Inducers include phenobarbital, carbamazepine, and phenytoin which could reduce BUP levels and lead to withdrawal symptoms though this has not been observed clinically, likely because the BUP metabolite nor-BUP also has partial agonist effects at the mu receptor.

Methadone

Methadone differs pharmacologically from BUP/NX in that it is a long-acting full agonist at the mu opioid receptor that produces cross-tolerance to superimposed opiates (e.g., heroin). As a full agonist, however, there is no clear ceiling effect to its respiratory suppressive effects and thus can cause overdose in opiate naïve people or when the rapidity of dose increase exceeds tolerance. To mitigate the risks of methadone exposure to opiate naïve individuals, methadone is highly regulated and directly observed daily dosing is required.

Methadone has multiple clinically significant drug-drug interactions with ART and medications used for treatment of tuberculosis. Methadone decreases clearance of zidovudine which can lead to increased zidovudine toxicity (e.g., anemia). Other commonly prescribed ART increase methadone metabolism (e.g., efavirenz, nevirapine, and lopinavir/ritonavir), potentially requiring high doses of methadone to relieve withdrawal symptoms, and requiring methadone dose tapering to prevent unintentional overdose when ART is stopped. Nearly all HIV-infected participants in Vietnam are prescribed at least one ART medication that requires methadone dose adjustments. Rifampin, an anti-tuberculosis agent commonly prescribed in Vietnam, decreases methadone levels and may require increased methadone doses to avoid withdrawal symptoms.

Potential Benefits

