We will conduct three sensitivity analyses. First, we will assume data are missing not at random and use single imputation of unsuppressed for missing VL data. Participants who are lost to follow-up will be imputed as treatment failures (i.e., not suppressed). Death from any cause and dropout will also be considered equivalent to non-suppression for the purposes of this analysis. Second, we will use multiple imputation with Markov-Chain Monte Carlo methods and “auxiliary variables” (i.e., covariates that are not part of the main analysis, but may help predict data missingness) to address missing data. We will include covariates associated with missingness at any time-points (using a relaxed p-value of 0.2) as auxiliary variables in our multiple imputation model. Finally, for our third sensitivity analysis, we will conduct a per-protocol analysis among participants who received at least one dose of study medication in the 90 days before each visit. If sensitivity analysis results change the primary outcome findings, we will report the results alongside our main analysis.

Secondary outcomes including binary ART initiation, ART adherence, and retention in HIV care will be analyzed using similar procedures. As these are superiority hypotheses, we will test them using two-tailed tests at an alpha level of .05.

Aim 2: Assess effect of clinic-based BUP/NX versus MMT referral on opioid use in HIV-infected participants with opioid dependence.

- **H2:** We hypothesize that participants randomized to BUP/NX will have a lower proportion of positive assessments for opioid use (self-report + UDS) at 12 months versus MMT referral

Overview. In Aim 2, we assess the effect of clinic-based BUP/NX on opioid use as measured by urine drug screens or any self-reported use in the last 30 days, assessed at 3, 6, 9, and 12 months following randomization.

Dependent variables. The primary dependent variable for Aim 2 will be the proportion of positive assessments for opioid use at 12 months, as measured by any self-reported opioid use or positive urine drug screen during the 12-month follow-up assessment (binary). We will consider secondary substance use outcomes including proportion of follow-up visits with a positive assessment for opioid use (proportion), and other illicit drug use (binary), and alcohol use (binary).

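### Capture of non-fatal overdose is uncertain and may differ by arm, no by-arm safety analysis is given, and benzodiazepine use has no urine confirmation

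*Combined protocol and SAP*

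**What the plan says.** **Risks named.** The background on clinic-based BUP/NX counts low overdose risk among its advantages. Under Risks and Benefits, the first BUP/NX risk listed is "death, which has been reported among people who abuse BUP in combination with benzodiazepines and other drugs"; the same section describes BUP/NX overdose risk as limited. The Methadone section says that "there is no clear ceiling effect to its respiratory suppressive effects and thus can cause overdose", and then gives the circumstances: lack of opioid tolerance, or dose increases that outrun tolerance.

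**Exposure measured.** The Biologic Data section says that "urine drug screens (morphine, methamphetamine, methadone, amphetamine, buprenorphine) will be collected and processed in the HIV clinic". Benzodiazepines are not among the five analytes. The survey has a domain called "Drug and alcohol use", and Table 2 schedules an "ASI-lite Table" at baseline and at 3, 6, 9 and 12 months. The items of neither are reproduced.

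**Events recorded.** Table 2 lists a "Fatal Overdose Form", as needed, and no form for non-fatal overdose. It also lists adverse event and serious adverse event eCRFs, as needed. Under Data and Safety Monitoring, "all Serious Adverse Events will require reporting in the data system", and only adverse events that are both mild and unrelated to study drug stay on paper. Under Risk of Underlying Conditions, however, HIV complications, substance-use-treatment events, hospitalizations and deaths go to study-specific forms and are not also reported as adverse or serious adverse events. They still go to the DSMB.

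**Analysis planned.** The Data Analysis section covers viral suppression, ART initiation, adherence, retention, substance use and qualitative work. It gives no by-arm analysis of overdose, deaths or adverse events.

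**The concern.** Overdose is the safety difference that the protocol itself draws between the two treatments. The trial is open-label, and the arms are managed in different places: BUP/NX by the HIV clinic's study physician, methadone by MMT staff. An event recorded only when someone happens to hear of it is more likely to be recorded where the participant is seen by study personnel for dosing. That could produce a spurious difference between arms or hide a real one.

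The natural safeguard for a non-fatal overdose is serious adverse event reporting. The underlying-conditions rule takes hospitalizations out of that route and sends them to forms that the assessment table does not clearly show. The most serious non-fatal overdoses, those admitted to hospital, are thus the ones whose place in the data is least certain.

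At stake is the completeness and evenness of the safety comparison, and how much it can say about adding BUP/NX to the treatment options. The noninferiority conclusion on viral suppression is not at stake.

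**Working it through.** The plan states no overdose rate or safety precision, so there is no figure to reproduce. The first three steps compare sections; the fourth shows the scale under assumed rates.

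**1. Where would each event be recorded?**
- *Fatal overdose:* the Fatal Overdose Form. Data and Safety Monitoring also treats death as a serious event to be telephoned to the PI within 24 hours and wants all serious adverse events in the data system, whereas the underlying-conditions rule says deaths are not also reported as such. The sections need reconciling, but a form exists.
- *Non-fatal overdose with hospitalization:* by the underlying-conditions rule, a study-specific form and no adverse event report; by the monitoring section, a serious adverse event report. Table 2 has no hospitalization form. The HIV Care Utilization Form might hold such data, but its content is not shown.
- *Non-fatal overdose without hospitalization:* the adverse event or serious adverse event eCRF, if reported. Both are as-needed forms, not scheduled questions.

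**2. Is capture the same in both arms?** Both arms have research visits at 3, 6, 9 and 12 months, but Table 2 schedules no overdose form at them. Between visits, BUP/NX participants come to the study clinic for dosing and MMT participants go to MMT programs. MMT charts are reviewed quarterly; the purposes given are receipt of ART, retention, and adherence to study treatment, and overdose is not mentioned. More complete capture in the BUP/NX arm is plausible. Its size cannot be derived from the documents.

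**3. What is known of benzodiazepine use?** No urine test is planned at any visit. Self-report is the remaining scheduled route, and whether its items cover benzodiazepines cannot be seen. For the secondary outcome on other illicit drugs, the panel can confirm only amphetamine-type use.

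**4. How much would wider capture add?** Inputs: 450 participants for about 12 months, so at most about 450 person-years. If the anticipated 20% attrition all fell at the start, 450 × 0.8 = 360. The overdose rates are assumptions; the documents give none. With E events split equally over equal person-time, the variance of the log rate ratio is 1/(E/2) + 1/(E/2) = 4/E, so the 95% interval runs a factor of exp(1.96 × √(4/E)) each way. Events are taken as whole numbers.

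| Event | Assumed rate per 100 person-years | E at 450 | Factor | E at 360 | Factor |
|---|---|---|---|---|---|
| Fatal | 0.5 | 2 | 16.0 | 2 | 16.0 |
| Fatal | 2 | 9 | 3.7 | 7 | 4.4 |
| Any overdose | 5 | 22 | 2.3 | 18 | 2.5 |
| Any overdose | 20 | 90 | 1.5 | 72 | 1.6 |

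For example, E = 9 gives exp(1.96 × 0.667) = exp(1.307) = 3.7. The formula is crude at 2 events, but the message is safe: fatal events alone are uninformative.

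**The case against.** The strongest reply is that a missing dedicated form is not missing capture. The underlying-conditions rule forbids duplicate reporting, not recording, and the DSMB still receives the data. Overdoses outside that rule fall under adverse event reporting, from which only mild and unrelated events are kept off the data system. A separate Data and Safety Monitoring Plan is cited and may define these events. Drug use is self-reported in both arms. All of this stands. It defeats the stronger reading that a reader might infer, namely that neither benzodiazepine exposure nor non-fatal overdose can be compared by arm. The documents do not support that: routes exist, and their content is partly unseen.

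Nor does the trial set out to test an overdose advantage. Its aims are HIV outcomes, opioid use and implementation, and the overdose statements are background and risk disclosure. The methadone warning is also conditional, and its reference to people without opioid exposure largely does not fit participants with opioid use disorder and an opioid-positive screen. So this is not a failure to test a stated hypothesis.

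A quarterly benzodiazepine strip would show use around the visit, not at the time of a death or over-sedation, and a positive result could reflect prescribed use. That makes the strip optional.

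The reply leaves three things unanswered: the two reporting rules pull in different directions for a hospitalized overdose, the receiving form is not identifiable in Table 2, and no by-arm safety analysis is given.

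**Conclusion.** The point holds as one of uncertain and possibly uneven capture, not of impossible comparison. A hospitalized non-fatal overdose may fall between two reporting systems; other non-fatal overdoses depend on event-driven reporting. Capture may favour the BUP/NX arm, by an amount the documents do not allow one to estimate. Benzodiazepine use has no urine confirmation and could at best be compared by self-report. Any by-arm comparison of either would be unplanned and possibly incomplete.

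The precision figures rest on assumed event rates, an equal split of events and, for the 450 person-year column, full follow-up. Even complete capture would leave a factor of about 2.3 each way at the low assumed rate, so the gain is better and more even safety data, not an assured test of a difference. The separate monitoring plan could settle part of this and should be checked first. This is an inexpensive improvement to make; the primary outcome is unaffected.

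**What to change.** 1. Widen the Fatal Overdose Form to any overdose, fatal or non-fatal, and ask it at the scheduled 3, 6, 9 and 12 month visits in both arms, keeping as-needed use between visits.
2. Reconcile Risk of Underlying Conditions with Data and Safety Monitoring so that each overdose, hospitalization and death has one named form, and show that form in Table 2.
3. Add to the Data Analysis section a table of overdoses and deaths by randomized arm, with person-time and confidence intervals.
4. Optionally, add a benzodiazepine strip to the urine already collected at Screening and at 3, 6, 9 and 12 months. Report it by arm as its own item, with prescribed use recorded, and do not count every positive as other illicit drug use.

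Cost: a short amendment and a few items per visit. The strip, if added, needs about 450 × 5 = 2,250 units, more with screen failures. These changes concern measurement and reporting only. If follow-up is already advanced, items 2 and 3 remain useful without new data collection.
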